#### 8.0 CLINICAL TRIAL MATERIAL MANAGEMENT

This section contains information regarding all medication and materials provided directly by the sponsor, and/or sourced by other means, that are required by the study protocol, including important sections describing the management of clinical trial material.

# 8.1 Study Medication and Materials

# 8.1.1 Dosage Form, Manufacturing, Packaging, and Labeling

In this protocol, the term study medication refers to all or any of the drugs defined below.

- Lubiprostone 24 µg capsules.
- Placebo capsules to match lubiprostone 24 μg.

Investigational material is encapsulated in clear orange soft gelatin capsules and packaged into 60 count high-density polyethylene (HDPE) bottles, including a rayon filler, induction sealed and closed with a child-resistant cap. Each bottle contains enough capsules to treat subjects for 28 days + a 2-day window during the Double-Blind Treatment Period, and will be labeled with a single-panel label including pertinent study information. As this study is double-blind, all study medication will be packaged, labeled, and dispensed in a blinded manner.

The bottle will contain an unique medication identification (MED ID) number and will be dispensed via the Interactive Web Response System (IWRS), with 1 bottle dispensed per subject.

An IWRS program will be used to manage inventory, assist the site in dispensing the proper investigational drug to the subjects, record accountability and support the return to sponsor or designee of these investigational drugs after study completion.

# 8.1.1.1 Investigational drug

Lubiprostone 24 µg and placebo will be supplied by the sponsor. All drugs supplied by the sponsor will be manufactured, tested, and released according to Good Manufacturing Practice (GMP).

#### 8.1.1.2 Rescue Medication

A total of 10 mg of bisacodyl suppository (or an equivalent drug) may be prescribed as a standard rescue medication if a subject has no adequate BM for 3 consecutive days during the study. When bisacodyl suppository does not improve constipation, glycerin enema (or equivalent drug) may be given. Subjects are instructed to complete their diaries before using these drugs. No rescue medication may be used within 24 hours before and 48 hours after the start of the Double-Blind Treatment Period (Day1).

# 8.1.2 Storage

Investigational drug must be kept in an appropriate, limited-access, secure place until it is used or returned to the sponsor or designee for destruction. Investigational drug must be stored under **CONFIDENTIAL** 

the conditions specified on the label, and remain in the original bottle until dispensed. A daily temperature log of the drug storage area must be maintained every working day.

Temperature excursion must be reported to the sponsor or designee.

# 8.1.3 Dose and Regimen

Subjects will be dispensed 1 bottle of study medication at Visit 2 (Day -1) and will be required to take 2 capsules daily, 1 in the morning and 1 in the evening with food. Subjects will be instructed to start study medication in the morning of the following day (Day 1).

Table 8.a describes the dose and regimen as it will be administered to each subject in each treatment group during the 4 weeks of the Double-Blind Treatment Period.

Table 8.aDose and Regimen

		Timing of Dose and Regimen	
Treatment Group	Dosage	Morning (AM)	Evening (PM)
Placebo	1 placebo capsule taken by mouth BID for 4 weeks	Administered orally with breakfast and 240 mL of	Administered orally with dinner and 240 mL
Lubiprostone	1 lubiprostone 24 μg capsule taken by mouth BID for 4 weeks	water	of water

#### 8.1.4 Overdose

An overdose is defined as a known deliberate or accidental administration of investigational drug, to or by a study subject, at a dose above that which is assigned to that individual subject according to the study protocol.

All cases of overdose (with or without associated AEs) will be documented on an Overdose page of the eCRF, in order to capture this important safety information consistently in the database. Cases of overdose without manifested signs or symptoms are not considered AEs. AEs associated with an overdose will be documented on AE eCRF according to Section 10.0, Pretreatment Events and Adverse Events.

Serious adverse events (SAEs) associated with overdose should be reported according to the procedure outlined in Section 10.2.2, Collection and Reporting of SAEs.

In the event of drug overdose, the subject should be treated symptomatically.

# 8.2 Investigational drug Assignment and Dispensing Procedures

The investigator or investigator's designee will access the IWRS at Screening/ Visit 1 to obtain the subject study number.

After study eligibility is confirmed (ie. at Visit 2), the investigator or the investigator's designee will utilize the IWRS to randomize the subject into the study. During this contact, the investigator or designee will provide the necessary subject-identifying information, including the

subject number assigned at Screening. The MED ID number of the investigational drug to be dispensed will then be provided by the IWRS.

If the investigational drug is lost or damaged, the site can request a replacement from IWRS. (Refer to IWRS manual provided separately.)

If a dose was missed, the subject is to leave the capsule in the bottle and resume regular administration at the next scheduled dose time. The subject is instructed to note the missing dose in the daily diary.

Instructions for subjects on how to store investigational drug will be provided by the investigator or investigator's designee.

Unused medication should be returned at Visit 5.

# 8.3 Randomization Code Creation and Storage

The sponsor or designee will generate the randomization schedule prior to the start of the study; IWRS will be used in a centralized fashion for subject randomization and study medication assignments. All randomization information will be stored in a secured area, accessible only by authorized personnel.

# 8.4 Investigational Drug Blind Maintenance

The investigational drug blind will be maintained using the IWRS.

# 8.5 Unblinding Procedure

The investigational drug blind shall not be broken by the investigator unless information concerning the investigational drug is necessary for the medical treatment of the subject. In the event of a medical emergency, if possible, the medical monitor should be contacted before the investigational drug blind is broken to discuss the need for unblinding.

For unblinding a subject, the investigational drug blind can be obtained by the investigator, by accessing the IWRS.

The sponsor must be notified as soon as possible if the investigational drug blind is broken. The date, time, and reason the blind is broken must be recorded in the source documents and the same information (except the time) must be recorded on the eCRF.

If any site personnel are unblinded, investigational drug must be stopped immediately and the subject must be withdrawn from the study.

# 8.6 Accountability and Destruction of sponsor-Supplied Drugs

Drug supplies will be counted and reconciled at the site before being returned to the sponsor or designee.

The investigator or designee must ensure that the sponsor-supplied drug is used in accordance with the protocol and is dispensed only to subjects randomized in the study. To document

appropriate use of sponsor-supplied drug (lubiprostone and matching placebo), the investigator or designee must maintain records of all sponsor-supplied drug delivery to the site, site inventory, dispensation and use by each subject, and return to the sponsor or designee.

Upon receipt of sponsor-supplied drug, the investigator or designee must verify the contents of the shipments against the packing list. The verifier should ensure that the quantity is correct, and the medication is in good condition. If quantity and conditions are acceptable, investigator or designee should acknowledge the receipt of the shipment by recording in IWRS. If there are any discrepancies between the packing list versus the actual product received, Takeda must be contacted to resolve the issue. The packing list should be filed in the investigator's essential document file.

The investigator or designee must maintain 100% accountability for all sponsor-supplied drugs received and dispensed during his or her entire participation in the study. Proper drug accountability includes, but is not limited to:

- Continuously monitoring expiration dates if the expiry date is provided to the investigator or designee.
- Frequently verifying that actual inventory matches documented inventory.
- Verifying that the log is completed for the MED ID used to prepare each dose.
- Verifying that all containers/ bottles used are documented accurately on the log.
- Verifying that required fields are completed accurately and legibly.

If any dispensing errors or discrepancies are discovered, the sponsor must be notified immediately.

The IWRS will include all required information as a separate entry for each subject to whom sponsor-supplied drug is dispensed.

The investigator or designee must record the current inventory of all sponsor-supplied drugs lubiprostone and matching placebo on a sponsor-approved drug accountability log. The following information will be recorded at a minimum: protocol number and title, name of investigator, site identifier and number, description of sponsor-supplied drugs, expiry date, date and amount dispensed including initials or signature of the person dispensing the drug, and the date and amount returned to the site by the subject, including the initials or signature of the person receiving the sponsor-supplied drug. The log should include all required information as a separate entry for each subject to whom sponsor-supplied drug is dispensed.

All study drugs that was not returned to the site by a subject must be investigated by the site and appropriately documented on the drug accountability log.

Prior to site closure or at appropriate intervals, a representative from the sponsor or its designee will perform sponsor-supplied drug accountability and reconciliation before sponsor-supplied drugs are returned to the sponsor or its designee for destruction. The investigator or designee will

retain a copy of the documentation regarding sponsor-supplied drug accountability, return, and/or destruction, and originals will be sent to the sponsor or designee.

The investigator will be notified of any expiry date or retest date extension of sponsor-supplied drug during the study conduct. On expiry date notification from the sponsor or designee, the site must complete all instructions outlined in the notification, including segregation of expired sponsor-supplied drug for return to the sponsor or its designee for destruction.

In the event of expiry date extension of sponsor-supplied drug already at the study site, sponsor-supplied drugs may be relabeled with the new expiry date at that site. In such cases, Takeda or its designee will prepare additional labels, certificates of analyses, and all necessary documentation for completion of the procedure at the sites.

#### 9.0 STUDY PLAN

### 9.1 Study Procedures

The following sections describe the study procedures and data to be collected. For each procedure, subjects are to be assessed by the same investigator or site personnel whenever possible. The Schedule of Study Procedures is located in Appendix A.

### 9.1.1 Informed Consent Procedure

The requirements of the informed consent are described in Section 15.2 and Appendix C.

Informed consent must be obtained prior to the subject entering into the study, and before any protocol-directed procedures are performed.

A unique subject identification number (subject number) will be assigned to each subject at the time that informed consent is obtained; this subject number will be used throughout the study.

## 9.1.2 Demographics, Medical History, and Medication History Procedure

Demographic information to be obtained will include age, sex, race as described by the subject, and smoking status of the subject at Screening.

Medical history to be obtained will include determining whether the subject has any significant conditions or diseases relevant to the disease under study that stopped at or prior to signing of informed consent. Ongoing conditions are considered concurrent medical conditions (see Section 9.1.11).

Medication history information to be obtained includes any medication relevant to eligibility criteria and efficacy/safety evaluation stopped at or within1 month prior to signing of informed consent.

### 9.1.3 Physical Examination Procedure

A baseline physical examination (defined as the assessment prior to first dose of investigational drug) will consist of the following body systems: (1) eyes; (2) ears, nose, throat; (3) cardiovascular system; (4) respiratory system; (5) gastrointestinal system; (6) dermatologic system; (7) extremities; (8) musculoskeletal system; (9) nervous system; (10) lymph nodes; (11) genitourinary system; and (12) other. All subsequent physical examinations should assess clinically significant changes from the assessment prior to first dose examination.

### 9.1.4 Weight, Height

A subject should have weight and height measured while wearing indoor clothing and with shoes off. Height will be measure at Visit 1 and weight will be measured at Visit 1 and 5. The Takeda standard for collecting height is centimeters without decimal places and for weight it is kilograms (kg) with 1 decimal place.

## 9.1.5 Vital Sign Procedure

Vital signs will include body temperature, respiratory rate, sitting blood pressure (resting more than 5 minutes), and pulse (bpm).

## 9.1.6 Primary Efficacy Endpoint

The primary efficacy endpoint is SBM frequency at Week 1, the data for which will be collected in a subject diary; see Appendix E. Subjects will be given a diary to complete at home, where they will record the date and time of each BM.

### 9.1.7 Secondary Efficacy Endpoints

### 9.1.7.1 SBM Frequency at Weeks 2, 3 and 4

This secondary endpoint will be collected as specified for the primary analysis.

## 9.1.7.2 Proportion of Subjects Who Have a SBM Within 24 Hours After First Dose

The proportion of subjects with an SBM within 24 hours after first dose in Week 1 will be assessed and derived from the data on SBMs collected in the subject diary.

## 9.1.7.3 Degree of Straining

For each subject, the degree of straining will be scored on a 5-point scale, with a higher score indicating more severe straining, and averaged for all SBMs at Weeks 1, 2, 3, and 4. The degree of straining for each SBM will be collected in the subject diary.

## 9.1.7.4 Stool Consistency

Stool consistency will be scored using the Bristol Stool Chart (see Appendix E) and the mean provided for all SBMs at Weeks 1, 2, 3 and 4. Stool consistency will be collected in the subject diary for each SBM recorded.

#### 9.1.7.5 Assessments of Abdominal Symptoms

The abdominal symptoms (bloating and discomfort upon waking in the morning) will be scored weekly on a 5-point scale, with a higher score indicating more severe symptoms. This will be assessed at Baseline and at Weeks 1, 2, 3, and 4. Subjects will be instructed to record weekly abdominal symptoms assessment in the diary. Diary entries will be reviewed at each study visit as per protocol schedule.

#### 9.1.7.6 Weekly Responder Rate

Weekly responder rate will be assessed at each week and will be derived from the data on SBMs collected in the subject diary.

Responder analysis will be performed at each week. A non-responder will be defined as any subject with a spontaneous BM frequency rate of less than 3 for a given week, any subject who dropped out during or prior to the given week due to lack of efficacy, or any subject who used rescue medication during or within 24 hours prior to the given week. Otherwise, the subject will be considered a responder. A responder with a spontaneous BM frequency rate  $\geq$  3 but <4 will be considered a moderate responder. Otherwise, the subject will be a full responder ( $\geq$  4 SBM).

### 9.1.8 Additional Endpoints

## 9.1.8.1 Quality of Life Evaluation

The PAC-QOL is a health related QOL instrument designed specifically to evaluate an adult subject's assessment of constipation over time. It is self administered assessment consisting of 28 items and is designed to cover the 2 weeks prior to the questionnaire being completed. Each item is scored from 0 to 4; a lower score is better. The 28 items are grouped into 4 subscales: physical discomfort, psychosocial discomfort, worries and concerns, and satisfaction.

The PAC-QOL will be assessed at Day -1 (prior to the start of study drug), mid-way through the Double-Blind Treatment Period on Day 15, and at the end of the Double-Blind Treatment Period, on Day 29.

## 9.1.8.2 Safety Endpoints

Safety endpoints include adverse events, vital signs, clinical laboratory tests, physical examinations, and body weight.

#### 9.1.9 Exploratory Endpoint

9.1.9.1

#### 9.1.10 Documentation of Concomitant Medications

Concomitant medication is any drug given in addition to the study medication. These may be prescribed by a physician or obtained by the subject over the counter. Concomitant medication is not provided by Takeda. At each study visit, subjects will be asked whether they have taken any medication other than the study medication (used from signing of informed consent through the end of the study), and all medication including vitamin supplements, over-the-counter medications, and oral herbal preparations, must be recorded in the eCRF.

## 9.1.11 Documentation of Concurrent Medical Conditions

Concurrent medical conditions are those significant ongoing conditions or diseases that are present at signing of informed consent. This includes clinically significant laboratory,

CONFIDENTIAL

electrocardiogram (ECG), or physical examination abnormalities noted at the screening examination. The condition (ie, diagnosis) should be described.

## 9.1.12 Procedures for Clinical Laboratory Samples

All samples will be collected in accordance with acceptable laboratory procedures. The maximum volume of blood at any single visit is approximately 8 mL, and the approximate total volume of blood for the study is 24 mL.

Details of these procedures will be provided in the Central Laboratory Manual.

Table 9.a presents the clinical laboratory tests that will be utilized during this study.

**Table 9.a** Clinical Laboratory Tests

Hematology	Serum Chemistry	Urinalysis
RBC	ALP	Qualitative urinalysis (a)
WBC with differential	Albumin	
Hemoglobin	ALT	Microscopic analysis
Hematocrit	AST	(only if positive dipstick
Platelets	Total bilirubin	results) (b)
MCV	Direct bilirubin	
MCH	Total protein	
RDW	Total Cholesterol	
	Triglyceride	
	Glucose	
	Creatinine	
	BUN	
	Creatine kinase	
	Uric acid	
	GGT	
	LDH	
	Potassium	
	Sodium	
	Chloride	
	Calcium	
	Phosphorous	
	Magnesium	
	TSH (Visit 1)	
	CRP (Visit 1)	

_	_		
11	4h	~~	
ι,	LH	ш	

Serum:	Urine:
Female subjects only:	Female subjects only:
Beta hCG (for pregnancy) Visits 1 and 5	hCG for pregnancy Visit 2
female subjects of childbearing potential only	female subjects of childbearing potential only.
	Drug screen for drugs of abuse at Visit 1

BUN=blood urea nitrogen, CRP= C-reactive protein, GGT= gamma-glutamyl transpeptidase, hCG=human chorionic gonadotropin, hpf=high-power field, LDH= lactic dehydrogenase, MCH=mean corpuscular hemoglobin, MCV=mean corpuscular volume, RBC= red blood cell, RDW=red (cell) distribution width, TSH= thyroid-stimulating hormone, WBC=white blood cell.

- (a) Qualitative urinalysis: pH, specific gravity, protein, glucose, occult blood, urobilinogen, bilirubin, ketone and leukocyte esterase.
- (b) Microscopic analysis: RBC/hpf, WBC/hpf, epithelial cells, casts, etc.

Blood is collected for hematology and blood biochemistry, and urine is collected for urinalysis at Visit 1 (Screening), and Visit 5 (at the completion of the Double-Blind Treatment Period), and, if applicable, at an Early Termination Visit. Women of childbearing potential undergo pregnancy test by serum at Visit 1 and 5 (or Early Termination Visit) and by urine at Visit 2. No pregnancy test is performed on women who have not menstruated for a year or longer.

The central laboratory will perform laboratory tests for hematology, serum chemistries, and urinalysis (excluding pregnancy tests). The results of laboratory tests will be returned to the investigator, who is responsible for reviewing and filing these results.

If subjects experience ALT or AST >3 ×ULN, follow-up laboratory tests (at a minimum, serum alkaline phosphatase, ALT, AST, total bilirubin, GGT, and INR) should be performed within a maximum of 7 days and preferably within 48-72 hours after the abnormality was noted.

(Please refer to Section 7.5 for discontinuation criteria, and Section 10.2.3 for the appropriate guidance on Reporting of Abnormal Liver Function Tests in relation to ALT or AST >3 ×ULN in conjunction with total bilirubin >2 ×ULN.)

If the ALT or AST remains elevated >3 ×ULN on these 2 consecutive occasions the investigator must contact the Medical Monitor for consideration of additional testing, close monitoring, possible discontinuation of study medication, discussion of the relevant subject details and possible alternative etiologies. The abnormality should be recorded as an AE (please refer to Section 10.2.3 Reporting of Abnormal Liver Function Tests for reporting requirements).

The investigator will maintain a copy of the laboratory accreditation and the reference ranges for the laboratory used.

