#### 7.1 Inclusion Criteria

Subject eligibility is determined according to the following criteria prior to entry into the study:

- 1. In the opinion of the investigator, the subject is capable of understanding and complying with protocol requirements.
- 2. The subject or, when applicable, the subject's legally acceptable representative signs and dates a written, informed consent form and any required privacy authorization prior to the initiation of any study procedures.
- 3. The subject has a history of constipation defined as having SBM frequency of less than 3 times per week on average for 6 months or longer and for whom the same SBM frequency is observed during the Screening Period.
- 4. The subject has had 1 or more of the symptoms associated with SBM (described below) for 6 months or longer at the start of Screening:
  - a) Scybalum stool or hard feces in at least 1 out of every 4 bowel movements.
  - b) Sensation of incomplete evacuation in at least 1 out of every 4 bowel movements.
  - c) Straining in at least 1 out of every 4 bowel movements.
- 5. The subject rarely has loose stools without the use of laxatives.
- 6. The subject is willing and able to keep a diary on his/her own and willing and able to complete a questionnaire.
- 7. The subject is male or female and aged 19 years or older, at the time of signing an informed consent.
- 8. A female subject of childbearing potential\* who is sexually active agrees to use routinely adequate contraception\* from signing of informed consent throughout the duration of the study and 14 days after the last dose of study drug.

\*Definitions and acceptable methods of contraception are defined in Section 9.1.13 Contraception and Pregnancy Avoidance Procedure and reporting responsibilities are defined in Section 9.1.14 Pregnancy.

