## 9.1.13 Contraception and Pregnancy Avoidance Procedure

From signing of informed consent, throughout the duration of the study, and for 14 days after last dose of study medication, female subjects of childbearing potential\* who are sexually active with a nonsterilized male partner\*\* must use adequate contraception. In addition they must be advised not to donate ova during this period.

\*Females NOT of childbearing potential are defined as those who have been surgically sterilized (hysterectomy, bilateral oophorectomy or tubal ligation) or who are postmenopausal (eg, defined as at least 1 year since last regular menses with an FSH >40 IU/L or at least 5 years since last regular menses, confirmed before any study medication is implemented).

\*\*Sterilized males should be at least 1 year postvasectomy and have confirmed that they have obtained documentation of the absence of sperm in the ejaculate.

An acceptable method of contraception is defined as one that has no higher than a 1% failure rate. In this study, where medications and devices containing hormones are included, the only acceptable methods of contraception are:

**Table 9.b** Acceptable Methods of Contraception

Barrier Methods (a)	Intrauterine Devices (IUDs)	Hormonal Contraceptives
Male condom PLUS spermicide.	Copper T PLUS condom or spermicide.	

 Implants.

 Hormone shot/injection.

 
Cap (plus spermicidal cream or jelly) PLUS male condom and spermicide.
 
	
 
Progesterone T PLUS condom or spermicide.
 
	

Combined pill.

Minipill.

 
Diaphragm (plus spermicidal cream or jelly) PLUS male condom and spermicide.
 
		

Patch.

Vaginal ring PLUS male condom and spermicide.

IUD=intrauterine device.

Subjects will be provided with information on acceptable methods of contraception as part of the subject informed consent process and will be asked to sign a consent form stating that they understand the requirements for avoidance of pregnancy and donation of ova during the course of the study.

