During the course of the study, regular serum and urine hCG pregnancy tests will be performed for women of childbearing potential only, and subjects will receive continued guidance with respect to the avoidance of pregnancy as part of the study procedures (Appendix A). In addition to a negative serum hCG pregnancy test at Screening, subjects also must have a negative urine hCG pregnancy test prior to dispensing of study medication at Visit 2.

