### 9.3.1 Screening Period

Subjects will be screened within 2 weeks prior to Randomization. Subjects will be screened in accordance with predefined inclusion and exclusion criteria as described in Section 7.0. See Section 9.1.15 for procedures for documenting screening failures.

Procedures to be completed at Screening (Visit 1) include:

- Sign informed consent.
- Record demographics, medical history, and medication history. Includes the results at Screening for IBS. The results of enema X-ray examination or total colonoscopy performed in the past 2 years are referred to in order to confirm organic disorders have been ruled out. For subjects who have no history or show no current evidence of weight loss, anemia, or

rectal bleeding, the examination results of the past 3 years may be used to rule out organic disorders.

- Perform physical examination.
- Measure vital signs, weight, and height.
- Record the use of concomitant medications, including previous use of laxatives/drugs used for constipation.
- Instruct subject to stop the use of all existing laxatives/drugs used for constipation.
- Document concurrent medical conditions.
- Pretreatment adverse events assessment.
- Collect blood and urine samples for laboratory tests and urine drug screen. Serum hCG pregnancy test is required for women of child-bearing potential only.
- Dispense study diary and provide instructions on diary completion.
- Distribute rescue medications prescription.
- Eligibility assessment (review Inclusion/ Exclusion criteria).
- Access IWRS to obtain subject number.
- Guidance on the avoidance of pregnancy and ova donation.

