  - c) That personal information (including personal health information) may be added to Takeda's research databases for purposes of developing a better understanding of the safety and effectiveness of the study medication(s), studying other therapies for patients, developing a better understanding of disease, and improving the efficiency of future clinical studies:
  - d) That subjects agree not to restrict the use and disclosure of their personal information (including personal health information) upon withdrawal from the study to the extent that the restricted use or disclosure of such information may impact the scientific integrity of the research; and

- e) That the subject's identity will remain confidential in the event that study results are published.
- 25. Female subjects of childbearing potential (eg, nonsterilized, premenopausal female subjects) who are sexually active must use adequate contraception (as defined in the informed consent) from Screening throughout the duration of the study. Regular pregnancy tests will be performed throughout the study for all female subjects of childbearing potential. If a subject is found to be pregnant during study, study medication will be discontinued and the investigator will offer the subject the choice to receive unblinded treatment information.
- 26. A statement that clinical trial information from this trial will be publicly disclosed in a publicly accessible website, such as ClinicalTrials.gov.

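### Section 9.1.12 waives every pregnancy test after a year without menses, but Section 9.1.13 does not treat one year alone as the end of childbearing potential

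*Protocol*

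**What the plan says.** Section 9.1.12 of the protocol gives two rules in consecutive sentences. The first sets testing by childbearing potential: "Women of childbearing potential undergo pregnancy test by serum at Visit 1 and 5 (or Early Termination Visit) and by urine at Visit 2". The second, which closes the paragraph, is a waiver: "No pregnancy test is performed on women who have not menstruated for a year or longer". The waiver names no cause of the amenorrhea, no age and no FSH value.

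Inclusion criterion 8 in Section 7.1 sends the reader elsewhere for the definition: "Definitions and acceptable methods of contraception are defined in Section 9.1.13 Contraception and Pregnancy Avoidance Procedure". Section 9.1.13 counts a woman as not of childbearing potential if she is surgically sterilized or "postmenopausal (eg, defined as at least 1 year since last regular menses with an FSH >40 IU/L or at least 5 years" (both periods run from the same event), and it wants the status "confirmed before any study medication is implemented". Later in the same section, after limiting tests to women of childbearing potential, it adds to the negative serum result at Screening that "subjects also must have a negative urine hCG pregnancy test prior to dispensing of study medication at Visit 2".

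The remaining instructions follow childbearing potential. Section 9.3.1 is typical: "Serum hCG pregnancy test is required for women of child-bearing potential only". Sections 9.3.2 and 9.3.4, Table 9.a, Appendix A footnote (i), Appendix C item 25 and SAP Table 7.a take the same line. None of them mentions a one-year exemption.

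**The concern.** Two rules decide who is tested, and they do not pick out the same women. Where they differ, a site cannot obey both: one sentence says not to test, while Section 9.1.13 makes a negative result a condition of dispensing.

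What is at stake is a safety safeguard and an eligibility check. Pregnancy is exclusion criterion 9 in Section 7.2 and a ground for immediate withdrawal in Section 7.5. The contraception duty does not replace the tests. It starts at consent and applies only to women who are sexually active with a nonsterilized male partner, so it cannot reveal a pregnancy that already exists. Section 9.1.12 also leaves pregnancy tests out of the central laboratory's work, so the documents show no central check that would notice a skipped test.

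**Working it through.** The plan states no figure to reproduce. The check is to apply both rules to each kind of woman and count the tests.

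**Inputs**

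- Waiver (Section 9.1.12): a year or longer without menstruating, whatever the cause.
- Definition (Section 9.1.13): sterilized; or at least 1 year since last regular menses with FSH above 40 IU/L; or at least 5 years since last regular menses. The postmenopausal limits follow eg.
- Test schedule (Section 9.1.12, Appendix A): serum at Visit 1 (Day -15), urine at Visit 2 (Day -1), serum at Visit 5 (Day 29) or Early Termination. The first dose is on Day 1.

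**Applying both rules to women who have not menstruated for at least a year**

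1. Surgically sterilized: no test under either rule. They agree.
2. At least 5 years since last regular menses: no test under either rule. They agree.
3. At least 1 year, with FSH above 40 IU/L on record: no test under either rule. They agree.
4. Non-sterilized, under 5 years since last regular menses, no such FSH on record, but judged postmenopausal by the investigator on other grounds: the eg leaves room for this, and then the rules agree.
5. Non-sterilized, under 5 years, and not postmenopausal, for example amenorrheic on an implant, injection or pill from the hormonal column of Table 9.b: Section 9.1.13 requires testing and the waiver forbids it. They conflict. Appendix C item 25 also puts her among those to be tested, since its own illustration is "Female subjects of childbearing potential (eg, nonsterilized, premenopausal female subjects) who are sexually active must use adequate contraception", and it then promises regular pregnancy tests to all women of childbearing potential.

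FSH appears in none of Table 9.a, Appendix A footnote (h) or SAP Table 7.a. Case 3 can therefore be shown only with a result from outside the planned panel.

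**Tests lost per randomized woman in case 5**

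- Scheduled: Day -15, Day -1 and Day 29, so 3 tests.
- Before Day 1: Day -15 and Day -1, so 2 of the 3. These are the only two checks before dosing.
- A woman who fails screening loses 1 test if she leaves after Visit 1. She can lose 2 if she fails at Visit 2, where the urine test is also listed.

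**Width of the disputed interval**

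The limits of 1 and 5 years suggest 5 - 1 = 4 years. That is only an upper bound, because the two sections run different clocks. Section 9.1.12 counts time without menstruating, and Section 9.1.13 counts time since the last *regular* menses. A woman 2 years past regular menses who bled irregularly 6 months ago, with no FSH value on record, is not waived by Section 9.1.12 and is to be tested under Section 9.1.13, so the rules agree for her.

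**The case against.** The best defence is that the sentence is shorthand for postmenopausal women and that the rest of the protocol makes this clear. It directly follows a rule about childbearing potential. The visit lists, Table 9.a, Appendix A, the consent elements and the SAP all use that rule, and Section 7.0 wants entry criteria and test results confirmed before dispensing on Day -1. The Section 9.1.13 limits are illustrative, so an investigator may call a woman with long amenorrhea postmenopausal without an FSH value. A woman in the hormonal-contraceptive example is using a method that Section 9.1.13 holds to a failure rate of no more than 1%. Section 4.1.3.3 reports reproductive toxicity only at doses far above the pharmacologically effective dose.

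Most of this stands, and it limits the weight of the point. It does not remove the contradiction. The sentence does not say postmenopausal, nothing in the documents makes one year without menses sufficient, and no reading makes a younger woman with contraceptive-induced amenorrhea postmenopausal after a year.

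A reader might infer two stronger claims. One is that the trial will treat women for a full course (2 capsules x 28 days = 56) with no pregnancy test at all. That requires a site to follow this one sentence over every other testing instruction, and the documents give no reason to expect it. The other is that every woman between 1 and 5 years from regular menses is wrongly exempted. The eg and the differing clocks rule that out.

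**Conclusion.** The concern holds as an inconsistency between two sections. Taken literally, the closing sentence of Section 9.1.12 removes all 3 scheduled hCG tests, 2 of them before the first dose, from some women whom Section 9.1.13 treats as of childbearing potential. It would let drug be dispensed to them without the negative urine test that Section 9.1.13 requires. The conflict is firm for non-sterilized women whose year of amenorrhea has a cause other than menopause. It is softer for women near menopause, where it depends on how the eg is read.

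The number affected cannot be derived, since neither document gives the expected age, menopausal status or contraceptive use of the women enrolled. The practical consequence depends on which instruction a site follows, and most of them lead to testing. The primary endpoint, sample size and error rate are untouched. The sentence should be corrected, but the point does not threaten the trial's conclusions.

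**What to change.** Delete the last sentence of the Section 9.1.12 paragraph and let Section 9.1.13 govern. Alternatively, replace it with: *Pregnancy tests are omitted only for women who are not of childbearing potential under Section 9.1.13.* Either is enough.

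As an option, add that a non-sterilized woman whose postmenopausal status has not been confirmed is tested. That settles how the eg works in practice. It also avoids adding FSH to the laboratory panel, because a woman without a documented value is simply tested.

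The cost is one sentence in an amendment, plus up to 3 hCG tests per affected woman, of types and at visits already in the schedule. Nothing in the sample size or analysis changes.
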